8 STUDY CALENDAR

1 cycle = 28 days (\pm 3 days unless otherwise specified)

Some study visits may be conducted remotely when remote telehealth visits do not present increased risk to the participant and all necessary data for the trial can be collected. The method of telehealth should be documented in the participants' charts. Visits that require study-related imaging, research lab samples, and/or pathology should be conducted in person.

Activity/Assessment	Screening	Baseline	Cycle 1					Cycles 2 to 6		Cycle 7 ²⁷	Cycle 10 ⁺²⁷	End of Treatment Visit (EOT)	Survival Follow-up ²³ (Every 3 mo.)
	Day -28 to Day -1	Day -7 to Day -1	D1	D3 ²²	D8	D15	D22	D1	D15	D1	D1	7 Days Post-Last Dose	
			\pm 1 day					\pm 2 days		\pm 2 days	\pm 3 days	\pm 2 days	
Informed consent ¹	X												
Eligibility criteria	X												
Demographics	X												
Medical history ²	X												
Medication history ²	X												
Screening symptom evaluation ³	X												
Height ⁴	X												
Weight	X		X					X		X	X	X	
Body Surface Area (BSA) ⁴	X												
Body Mass Index (BMI) ⁴	X		X					X		X	X	X	
Vital signs ⁵	X		X					X		X	X	X	
Physical examination ⁶	X		X					X		X	X	X	
DIPSS risk assessment ⁷	X												
ECOG performance status ⁸	X							X		X	X	X	
Optional Ophthalmic exam ⁹	X							ACI					X
12-lead ECG ¹⁰	X							ACI					X
CBC with differential ¹¹	X	X ¹¹			X	X	X	X	X	X	X	X	

Activity/Assessment	Screening	Baseline	Cycle 1					Cycles 2 to 6		Cycle 7 ²⁷	Cycle 10 + ²⁷	End of Treatment Visit (EOT)	Survival Follow-up ²³ (Every 3 mo.)
	Day -28 to Day -1	Day -7 to Day -1	D1	D3 ²²	D8	D15	D22	D1	D15	D1	D1	7 Days Post-Last Dose	
Thyroid stimulating hormone (TSH)	X							ACI					
Complete serum chemistry ¹²	X							X		X	X	X	
Limited serum chemistry ¹³				X	X								
Coagulation tests ¹⁴	X											X	
MRI (or CT abdomen) ¹⁵		X						X ¹⁵		X	X ¹⁵	X ¹⁵	
Chest radiograph ¹⁶	X							ACI					
Serum pregnancy test ¹⁷		X											
Bone marrow and peripheral blood for local pathology review ¹⁸	X									X	X ¹⁸	X	
Bone marrow and peripheral blood for central pathology review ¹⁸	X									X		X	
Bone marrow aspirate for CD34 section and testing,	X									X		X	
Selinexor administration ¹⁹			See administration table below										
Blood draw for PDn testing ²⁰							X ²⁰						
Adverse events								X					
Concomitant medication								X					
Nutritional consultation ²¹	X							ACI					
Telephone contact ^{22,23}			X ²²										X ²³
MPN-SAF TSS ²⁴		X		X	X			X		X	X	X	
IWG-MRT assessment ²⁵		X						X ²⁵		X	X	X	
Peripheral blood sample for cytokine profile ²⁶		X						X ²⁶		X ²⁶		X	
Peripheral blood sample for JAK2 V617F, MPL and		X						X ²⁶		X ²⁶		X	

Activity/Assessment	Screening	Baseline	Cycle 1					Cycles 2 to 6		Cycle 7 ²⁷	Cycle 10 + ²⁷	End of Treatment Visit (EOT)	Survival Follow-up ²³ (Every 3 mo.)
	Day -28 to Day -1	Day -7 to Day -1	D1	D3 ²²	D8	D15	D22	D1	D15	D1	D1	7 Days Post-Last Dose	
CALR exon 9 mutations allele burden ²⁶												± 2 days	± 14 days

Procedure	Day 1 of each cycle	Day 8 of each cycle	Day 15 of each cycle	Day 22 of each cycle
Selinexor administration ¹⁹	In clinic	In clinic for C1 At home for C2+	In clinic for C1 At home for C2+	At home for all cycles

ACI = As clinically indicated

- 1 Prior to the first study-specific measures.
- 2 Review of medical history and medication history, from the 12 months before screening, but incorporating, in full, prior lines of therapy regardless of date of occurrence. Including details of all therapies for myelofibrosis (start/stop dates, best response, disease progression during/after therapy, discontinuations due to intolerance/toxicity, etc.).
- 3 Using Screening Symptoms Form, see Appendix 6
- 4 Body Surface Area (BSA) and height will be collected at screening only. Screening height will be used to calculate BMI at all future visits.
- 5 To include blood pressure, pulse, temperature, and oxygen saturation.
- 6 All physical examinations (PE) must include spleen palpation. Symptom-directed limited PE can be performed outside of screening and EOT.
- 7 See Appendix 8
- 8 ECOG performance status assessments will be done on D1 of each Cycle, however the assessment for C1D1 may be done during Screening or pre-dose C1D1.
- 9 Full ophthalmic examination is optional at baseline and the final visit, and, if clinically indicated, during the study. Prior to dilation, best corrected visual – acuity, slit lamp examination including tonometry, following dilation; fundoscopy and slit lamp to document lens clarity – if a cataract/lens opacity is seen during the examination, the cataract/lens opacity will be graded according to a Grade 1-4 system (see Appendix 2)
- 10 ECG will be performed during Screening (or pre-dose C1D1) and the EOT Visit and as clinically indicated throughout the study.
- 11 CBC with differential includes hemoglobin, hematocrit, mean corpuscular volume, mean corpuscular hemoglobin, mean corpuscular hemoglobin concentration, white blood cell (WBC) count, WBC differential, RBC count, lymphocytes, monocytes, neutrophils, band neutrophils, eosinophils, basophils, platelets. WBC differential may be automated or manual as per institutional standards. Reticulocytes may be done only when clinically indicated. The baseline CBC need not be repeated if the screening CBC is performed within 7 days of C1D1.
- 12 Complete serum chemistry includes limited serum chemistry (as defined below) as well as, phosphate, magnesium, LDH, amylase, lipase, and uric acid. It is due at Screening or C1D1, then D1 of each subsequent Cycle, and EOT visit.

- 13 Limited chemistry includes sodium, potassium, chloride, calcium, bicarbonate, BUN, creatinine, glucose, total protein, albumin, ALT, AST, alkaline phosphatase, and total bilirubin. It is due at C1D8 and C1D15.
- 14 Includes prothrombin time (PT), international normalization ratio (INR), and activated partial thromboplastin time (aPTT).
- 15 Spleen volume will be measured by MRI (or CT abdomen if MRI is contraindicated) at screening, at C4D1 after completion of 3 cycles and at C7D1 after completion of 6 cycles, allowing up to 4 weeks after cycle 7 D1. Additional MRIs will be performed for patients continuing on study treatment at cycle 10 D1, cycle 13 D1, cycle 19 D1, C25D1 to assess spleen volume. Imaging modality should remain consistent throughout study for each patient. Screening MRI should be completed \leq 14 days prior to C1D1. An additional MRI will be performed at the End of Treatment for all patients including those who do not complete at least 6 cycles of study treatment unless death occurs. CT abdomen is acceptable if MRI is contraindicated for estimation of spleen volume.
- 16 Both posteroanterior and lateral films should be obtained at baseline. Note that this test does not need to be repeated if results are available from a test performed within 30 days prior to start of therapy. This test serves as a baseline in the event that patients develop any adverse events during the study.
- 17 For women of childbearing potential; negative serum β -hCG pregnancy test within 3 days of C1D1.
- 18 Bone marrow biopsies and aspirates will be obtained at \leq 42 days before C1D1, C7D1 (\pm 7 days), and EOT. Additional bone marrow biopsies will be performed at C19D1 and then every 12 cycles after that until treatment discontinuation.
- 19 Study drug administration will take place on a weekly basis and will be done in clinic at C1D1, and on the first day of each subsequent cycle. Patients will be instructed to take their dose of study drug at home on D8, D15, and D22 of each subsequent cycle.
- 20 Blood draws for PDn analysis will be collected at either C2D1 or C3D1 pre-dose (within 10 minutes prior to dose) and 4 hours post-dose (\pm 10 min)
- 21 It is strongly recommended that patients be given nutritional consultation to discuss food recommendations and strategies for managing potential nausea and appetite changes experienced with selinexor. Nutritional consultation can be done by study nurse/clinician face-to-face or by the HCI Wellness Center or site equivalent or over the telephone. These consultations should be continued during study therapy as clinically indicated.
- 22 Telephone call (or visit) with patient to evaluate supportive care medications and adverse events, and to adjust supportive care as appropriate. The telephone contact with the patient must take place on Day 3 (\pm 1 day) following the C1D1 selinexor dosing. If available, survival follow up data may be collected from patient medical record review in lieu of a telephone call.
- 23 After study discontinuation, a telephone call will be made to the patient (or the patient's family) every 3 months to inquire about the patient's disease status, well-being, and information on any antineoplastic therapies utilized since discontinuation of selinexor study treatment until 24 months after initiation. If available, survival follow up data may be collected from patient medical record review in lieu of a telephone call
- 24 MPN SAF TSS evaluation will be performed at baseline and at each subsequent clinic visit (C1D8, C1D15, C2D1 and D1 of every subsequent cycle up to cycle 7 and every 3 cycles thereafter and EOT. Patients will be given copies of the evaluation form for time points which do not coincide with a study visit and will be asked to return the forms at their next visit.
- 25 Disease status and/or response by IWG-MRT will be assessed at C4D1, C7D1, C10D1, C13D1, C19D1, C25D1 and EOT.
- 26 Peripheral blood sample for cytokine profile, mutation allele burden will be collected at baseline, C4D1, C7D1, and at the EOT visit.
- 27 Starting with Cycle 7, patients only need to return to clinic every three months unless earlier follow up is necessary per treating physician's discretion.

9 STUDY PROCEDURES

Some study visits may be conducted remotely when remote telehealth visits do not present increased risk to the participant and all necessary data for the trial can be collected. The method of telehealth should be documented in the participants' charts. Visits that require study-related imaging, research lab samples, and/or pathology should be conducted in person.

9.1 Screening Evaluations

All screening procedures must be completed \leq 28 days of C1D1. Screening procedures include:

- Informed consent
- Demographics
- Inclusion and exclusion criteria
- Review of medical history and medication history, from the 12 months before screening, but incorporating, in full, prior lines of therapy regardless of date of occurrence.
- Vital signs, height, weight, BSA, and BMI
- Physical examination including spleen size by palpation
- ECOG performance status (Appendix 1)
- DIPSS risk assessment (Appendix 8)
- Screening symptoms assessment (Appendix 6)
- Nutritional consult
- Optional Ophthalmologic exam (Appendix 2)
- Laboratory assessments:
 - CBC with differential (including reticulocytes if clinically indicated)
 - Complete serum chemistry to include:
 - CMP: sodium, potassium, chloride, carbon dioxide, alkaline phosphatase, AST, ALT, BUN, glucose, creatinine, calcium, total protein, albumin, total bilirubin (direct and indirect bilirubin must be obtained if total bilirubin is $\geq 1.5 \times$ ULN)
 - Phosphorus, magnesium, uric acid, LDH, amylase, lipase
 - Thyroid stimulating hormone
 - Coagulation tests to include PT, INR, and aPTT
- Serum pregnancy test (for women of childbearing potential, see Section 7.4)
- 12-lead ECG
- Chest X-ray
- Bone marrow biopsy and aspiration \leq 42 days before cycle one day one (can also be performed during the baseline visit). The study team will follow instructions in the lab manual for shipping tissue for central review.
- Standard of care procedures (e.g., blood count, serum chemistry) performed during this period should not be repeated and will be used for study purposes.

9.2 Baseline Evaluations

All baseline procedures must be completed \leq 7 days of C1D1. Baseline procedures include:

- Laboratory assessments:
 - CBC with differential (including reticulocytes if clinically indicated) – does not need to be repeated if screening CBC test has been performed within that same timeframe.
 - Serum pregnancy test \leq 72 hours prior to treatment initiation (for women of childbearing potential, see Section 7.4) – does not need to be repeated if screening pregnancy test has been performed within that same timeframe.
- MRI (or CT abdomen if MRI is contraindicated) \leq 14 days of C1D1 for estimation of spleen volume. Imaging modality should remain consistent throughout study for each patient.
- IWG-MRT assessment.
- MF symptom burden evaluation using the MPN-SAF TSS questionnaire (Appendix 7)
- Peripheral blood samples for cytokine profiling
- Peripheral blood samples for evaluation of *JAK2*, *MPL*, and *CALR* mutant allele burden

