1 OBJECTIVES

1.1 Primary Objective

To assess the efficacy of selinexor on spleen volume reduction in subjects with myelofibrosis (PMF, PET-MF, or PPV-MF) refractory or intolerant to ruxolitinib and/or any other experimental JAK1/2 inhibitors.

Primary Endpoint:

Response rate defined as the proportion of subjects with $\geq 35\%$ reduction in spleen volume as measured by MRI or CT abdomen from baseline to after six cycles of treatment. Patients who do not complete six cycles of therapy will be considered non-responders, but their data will still be reported. Patients who do not complete six cycles of treatment will receive an MRI at cycle 7 day 1, or at discontinuation of therapy (see section 11.4.2).

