Until 2012, MF treatment was limited to chemotherapy to control myeloproliferation (hydroxyurea, busulfan), supportive care measures such as cytokines to improve cytopenias (erythropoietin, G-CSF), and prednisone or immunomodulatory drugs (thalidomide and lenalidomide).¹⁶ The discovery of *JAK2*^{V617F} mutations in MF patients led to the development of ruxolitinib (RUX), a JAK1/2 inhibitor, which was approved in 2012 for high-risk and intermediate-2 risk MF patients. Two large randomized Phase 3 studies conducted in the United States and Europe showed superiority of RUX over placebo or best available therapy (BAT) in major endpoint (spleen volume reduction) and improvement in constitutional symptoms and QoL.^{17,18} In a more recent update, a trend toward improved overall survival was reported. However, some patients demonstrate inadequate response to RUX or develop progressive increase in spleen size after an initial response (refractory disease). Additionally, thrombocytopenia frequently limits dose intensity and renders many patients ineligible for

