5.2 Exclusion Criteria

Yes/No (Response of “yes” = patient ineligible)

- 5.2.1 Prior exposure to a SINE compound, including selinexor.
- 5.2.2 Patients who are below their ideal body weight and would be unduly impacted by changes in their weight, in the opinion of the investigator, will be excluded.
- 5.2.3 Uncontrolled active infection requiring parenteral antibiotics, antivirals, or antifungals \leq 1 week prior to C1D1. Patients on prophylactic antibiotics or with a controlled infection \leq 1 week prior to C1D1 are eligible.
- 5.2.4 Radiation, chemotherapy, immunotherapy, or any other anticancer therapy (including investigational therapies) \leq 2 weeks
- 5.2.5 Ruxolitinib or other JAK1/2 inhibitors \leq at least 3 days or 5 half-lives prior to C1D1.
- 5.2.6 Major surgery \leq 4 weeks prior to C1D1.
- 5.2.7 Known active hepatitis A, B, or C infection; or known to be positive for hepatitis C virus ribonucleic acid (RNA) or hepatitis B virus surface antigen.
- 5.2.8 Any active gastrointestinal dysfunction interfering with the patient's ability to swallow tablets, or any active gastrointestinal dysfunction that could interfere with absorption of study treatment.
- 5.2.9 Any life-threatening illness, organ system dysfunction, or serious psychiatric, medical, or other conditions/situations which, in the investigator's opinion, could compromise a patient's ability to give informed consent, safety, or compliance with the protocol.
- 5.2.10 Contraindication to any of the required concomitant drugs or supportive treatments.
- 5.2.11 Subjects taking prohibited medications as described in Section 6.3. Following discontinuation of prohibited medications, a washout period is required prior to initiating study treatment (the duration of the washout must be as clinically indicated, e.g., at least five half-lives).
- 5.2.12 Subjects who are breastfeeding and unwilling to stop while on study.

I certify that this patient meets all inclusion and exclusion criteria for enrollment onto this study.

Investigator Signature

Date

Time

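### The baseline spleen scan is not tied to the last JAK-inhibitor dose, so the 35% response threshold may be measured from an on-drug volume in some patients and an off-drug volume in others

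*Combined protocol and SAP*

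**What the plan says.** The primary endpoint (section 1.1) is the proportion of patients with at least a 35% "reduction in spleen volume as measured by MRI or CT abdomen from baseline to after six cycles of treatment". One pretreatment scan per patient fixes the denominator.

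- **When the scan may be taken.** Section 9.2 sets a limit of "14 days of C1D1 for estimation of spleen volume". Footnote 15 of the study calendar repeats it: "Screening MRI should be completed" no more than "14 days prior to C1D1. An additional MRI will be performed at the End of Treatment". Section 9.3.5 gives the same 14 days. The opening line of 9.2 ("All baseline procedures must be completed") and the calendar's baseline column, where the MRI sits, allow only 7 days.
- **When the JAK inhibitor must stop.** Exclusion 5.2.5 excludes use within "at least 3 days or 5 half-lives prior to C1D1". It does not say which of the two limits governs.
- **A neighbouring rule.** Exclusion 5.2.4 applies a 2-week limit to "Radiation, chemotherapy, immunotherapy, or any other anticancer therapy (including investigational therapies") and does not say whether JAK inhibitors fall under it.
- **What the drug does.** Section 2.1 reports that two phase 3 studies "showed superiority of RUX over placebo or best available therapy (BAT) in major endpoint (spleen volume reduction").
- **What is already recorded.** Calendar footnote 2 requires start and stop dates for all myelofibrosis therapies.

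No section requires the scan to follow the last JAK-inhibitor dose, asks for a repeat scan after stopping, or plans an analysis by drug status at the scan.

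**The concern.** The washout is counted back from C1D1, while the scan has its own, longer window. Two patients who both follow the protocol can have baselines of different kinds: one scanned while still taking a drug that the protocol credits with shrinking the spleen, the other scanned after stopping it. If volume rises once the drug is withdrawn, the first patient must undo that rise before any of the 35% is credited to selinexor. The second carries less of this burden, or none.

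The situation falls within the intended population. Inclusion 5.1.5 admits patients with an inadequate response after at least 3 months of JAK-inhibitor treatment, judged on spleen size at screening, so some may still be taking the drug then.

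At stake are the response estimate, the percent change in spleen volume (a secondary endpoint measured from the same scan), and how a narrowly negative result would be read.

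**Working it through.** **1. The plan's own figure.** Section 11.2: 18 evaluable patients, null rate 15%, alternative 42%, reject at 6 or more responders.

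- P(X ≥ 6 | n = 18, p = 0.15) = 0.042, within the one-sided 0.05.
- P(X ≥ 6 | n = 18, p = 0.42) = 0.837, against 83% stated. It reproduces.
- A cut-off of 5 would give a type I error of 0.121, so 6 is the right cut-off.

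**2. The timing gap.** Take the 3-day limit as governing. A patient may be on drug until about day −4, so a scan from day −14 to day −4 can be on-drug: 11 calendar days. Under the 7-day window the exposed days are −7 to −4. The gap narrows but does not close.

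**3. Effect on the threshold.** Let g be the fractional rise in spleen volume caused by withdrawal after the scan. If the scan reads V, the off-drug size is V(1 + g). A recorded 35% reduction means a final volume of 0.65V, so the reduction needed from the off-drug size is 1 − 0.65/(1 + g). A true 35% reduction from the off-drug size would be recorded as 1 − 0.65(1 + g).

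**4. Illustrative effect on power.** Three inputs are assumptions, because the documents give none of them: g; half of baselines on-drug; and percent reduction from the off-drug size Normal with SD 25 points. A fourth choice is to attach the plan's 42% to the off-drug baseline. The mean is then 0.35 − 0.25 × 0.2019 = 0.2995. For g = 10%:

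- Threshold: 1 − 0.65/1.10 = 0.409.
- Response rate with an on-drug baseline: P(Z ≥ (0.409 − 0.2995)/0.25) = 0.331.
- Mixed rate: 0.5 × 0.331 + 0.5 × 0.42 = 0.375.
- Power: P(X ≥ 6 | 18, 0.375) = 72.4%.

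| g (assumed) | Reduction needed | True 35% recorded as | Response rate, on-drug baseline | Mixed rate | Power |
|---|---|---|---|---|---|
| 0 | 35.0% | 35.0% | 42.0% | 42.0% | 83.7% |
| 1% | 35.6% | 34.4% | 41.0% | 41.5% | 82.6% |
| 2% | 36.3% | 33.7% | 40.0% | 41.0% | 81.5% |
| 5% | 38.1% | 31.8% | 37.2% | 39.6% | 78.2% |
| 10% | 40.9% | 28.5% | 33.1% | 37.5% | 72.4% |

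**5. Sensitivity to the model.** With a log-normal volume ratio instead (log-SD 0.2 to 0.5), half on-drug and g = 10%, power runs from 59% to 75%. With a quarter on-drug and g = 5%, it runs from 78% to 82%. The direction is stable; the size depends on what is assumed.

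**The case against.** **Regrowth needs time off drug.** The 11 days in which a scan can be on-drug are not 11 days of regrowth. A patient scanned on day −14 who stops 3 days before C1D1 has only about 3 drug-free days before selinexor starts. This stands. It also limits the remedy: a scan 0 to 3 days after the last dose captures only part of any slow regrowth, and the rest falls after C1D1.

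**Exposure may be limited.** Patients who stopped before screening, as many intolerant patients will have, cannot have an on-drug baseline. Refractory patients may have little drug effect left to lose. This stands, and the documents do not show how many patients are affected.

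**The power figure is not wrong.** A reader might infer that 83% presupposes off-drug baselines, or that the trial is underpowered. Section 11.2 supports neither: it gives power for a 42% response rate on the endpoint as defined, and does not tie that rate to a drug-free baseline. With 1% to 2% regrowth and half of baselines on-drug, the loss is only 1 to 2 points.

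**The dates are already held.** A reader might infer that drug status at the scan cannot be recovered. Footnote 2 collects the stop dates.

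**The baseline is defensible.** Appendix 5 refers progression to the pretreatment baseline, and measuring from the patient's actual state before selinexor is a reasonable choice. The difficulty is that the plan leaves that state to vary between patients and does not report it.

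**A mid-trial change splits the cohort.** Twelve of 24 patients had been treated by version 7 (section 2.3.3), so tightening the rule gives later patients a different baseline rule. This is a real cost. The proposed tabulation covers everyone and would make the difference visible.

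**Conclusion.** The point holds as a gap in the definition of baseline. The text permits on-drug and off-drug reference scans for the same 35% cut and plans no analysis to tell them apart. That JAK inhibition lowers spleen volume is in the documents; that volume rises after stopping is a reasonable inference. How much and how fast it rises is unknown.

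Any bias runs against selinexor, so it bears on the response estimate and power and does not inflate type I error. Under the stated assumptions the loss of power runs from about 1 point (1% regrowth) to about 11 points (10% regrowth); with no regrowth there is none. These figures are illustrations and not a forecast. The case for acting is that the remedy is cheap, not that a large loss has been shown.

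**What to change.** 1. **Patients not yet enrolled.** In 9.2 and calendar footnote 15, require the baseline MRI to be taken after the last JAK-inhibitor dose and as close to C1D1 as feasible within the existing window. The washout rule stays as it is, and no scan is added. The cost is tighter scheduling: with a minimum washout the scan has about 3 days to fit into. This reduces the problem without removing it, because regrowth may continue after C1D1.
2. **All patients.** From the stop dates collected under footnote 2, tabulate the interval from last JAK-inhibitor dose to baseline scan. Report the primary endpoint and percent change in spleen volume by on-drug or off-drug baseline, as a descriptive sensitivity analysis added to section 11.5. The cost is one table and no new data field. With at most 24 patients it can show a pattern but cannot test one.
3. **Text.** Reconcile the 7-day and 14-day MRI windows. Reconcile 5.2.4 with 5.2.5, and state which of the two limits in 5.2.5 governs. The sponsor should settle what was intended.
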